#### 5.2.4.2 Adverse event collection and reporting

##### 5.2.4.2.1 AE Collection

The investigator shall maintain and keep detailed records of all AEs in the patient files. The following must be collected and documented on the appropriate CRF(s) by the investigator:

- From signing the informed consent onwards until the individual patient's end of study (16 weeks after last dose of spesolimab, or at the time of withdrawal of participation): all AEs (serious and non-serious) and all AESIs.
- After the individual patient's end of study: the investigator does not need to actively monitor the patient for new AEs but should only report any occurrence of cancer and trial drug-related SAEs and trial drug-related AESIs of which the investigator may become aware of by any means of communication, e.g. phone call. Those AEs should however not be reported in the CRF.
- Upon patient re-entry into the trial, the patient should be re-evaluated to ensure that eligibility criteria are still met and the overall trial is still running in order to assess AEs (serious and non-serious) and AESIs.

##### Vital Status Data Collection

Patients who discontinue trial medication or participation prematurely, who agree to be contacted further but do not agree to physical visits, should be followed up as described in section [3.2.4.1](#), discontinuation of trial medication and assessment. Thus, for patients who discontinue trial medication or participation prematurely but agree to be contacted by phone for a last follow-up assessment at 16 weeks after last drug intake, the investigator must report any occurrence of cancer, all deaths / fatal AEs regardless of relationship, and trial drug-related SAEs and and trial drug-related AESIs the investigator becomes aware of.

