#### 3.2.4.1 Discontinuation of trial medication and assessment

An individual patient will discontinue treatment if:

- The patient wants to discontinue trial treatment. The patient will be asked to explain the reasons but has the right to refuse to answer.
- The patient has repeatedly shown to be non-compliant with important trial procedures and, in the opinion of both the investigator and sponsor representative, the safety of the patient cannot be guaranteed as he / she is not willing or able to adhere to the trial requirements in the future.
- The patient needs to take concomitant medication that interferes with the safety of the investigational medicinal product.
- The patient can no longer receive treatment for medical reasons such as surgery, adverse events, other diseases, or pregnancy.
- If a DILI alert (as defined in Section [5.2.4.1.4](#)) is detected without identification of an alternative cause in the work-up according to the “DILI checklist”, the patient should not receive subsequent doses of investigational medication. (If alternative cause is identified and patient has recovered according to investigator assessment, treatment can be restarted after consultation with the sponsor.)
- If peripheral neuropathy is suspected, treatment with spesolimab should be temporarily discontinued until a full neurological investigation has been conducted. After completion of the neurological investigation, treatment can be restarted based on medical judgement of the investigator.
- For individual stopping rules related to specific adverse events, please see Section [4.2.1](#) “Other treatments and emergency procedures.”

If new efficacy / safety information becomes available, Boehringer Ingelheim will review the benefit-risk-assessment and, if needed, pause or discontinue the infusion/treatment for all patients or take any other appropriate action to guarantee the safety of the patients participating in the trial.

If a patient wants to discontinue the trial participation, the investigator should request that the patient consent to be contacted, at least by phone, for a final follow-up assessment at 16 weeks after last drug intake. Where possible, any new or changes in previously reported AEs and concomitant therapies should be recorded at this assessment, as indicated in section [6.1.3](#). Specific information to be collected at the 16-week assessment in patients who have discontinued trial medication or assessment is detailed in section [5.2.4.2.1](#).

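### For patients who leave early but accept the 16-week call, the protocol conflicts on which adverse events are collected and whether they enter the eCRF

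*Combined protocol and SAP*

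**What the plan says.** Three texts govern the patient who ends participation early, will not attend visits, and agrees to be telephoned 16 weeks after the last dose.

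- **Section 3.2.4.1.** The investigator asks a patient who wants to leave to accept a final follow-up contact, at least by phone. "Where possible, any new or changes in previously reported AEs and concomitant therapies should be recorded at this assessment". This is to be done as in section 6.1.3, where AEs at every visit, including phone and video visits, go into the chart and the eCRF. The section then passes the detail on: "Specific information to be collected at the 16-week assessment in patients who have discontinued trial medication or assessment is detailed in section" 5.2.4.2.1.
- **Section 5.2.4.2.1, AE Collection.** "The following must be collected and documented on the appropriate CRF(s) by the investigator": from consent until the patient's end of study, which is 16 weeks after the last dose "or at the time of withdrawal of participation): all AEs (serious and non-serious) and all AESIs". After end of study the investigator "should only report any occurrence of cancer and trial drug-related SAEs and trial drug-related AESIs" that come to notice. "Those AEs should however not be reported in the CRF".
- **Section 5.2.4.2.1, Vital Status Data Collection.** Patients "who agree to be contacted further but do not agree to physical visits, should be followed up as described in section" 3.2.4.1. The next sentence, worded as a consequence, says that for those who accept the call the investigator "must report any occurrence of cancer, all deaths / fatal AEs regardless of relationship, and trial drug-related SAEs" and drug-related AESIs. It names no place of recording.

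Flow Chart footnote 2 asks for an early end-of-study visit when a patient refuses to return, and for safety information by phone at 16 weeks, without saying which information. The endpoints (2.1.2, 2.1.3) are TEAEs, treatment-emergent SAEs and treatment-emergent AESIs. Section 7.1.1 counts all AEs from the start of treatment to 16 weeks after the last dose, in all treated patients.

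**The concern.** The call falls at the end of the window that the analysis uses, so for these patients it is the last chance to complete the endpoint data. A site looking for the operative rule is sent from 3.2.4.1 to 5.2.4.2.1 and, in the Vital Status paragraph, back again. It ends at a list filtered by causality and seriousness. That list has the same content as the one for events after end of study, with deaths added, and events on the latter list are barred from the CRF. The endpoints carry no such filter. Sites could therefore collect different things at the same call, and the tables would not show it.

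**Working it through.** The plan states no figure on this point, so the check is a comparison of texts, followed by one calculation of calendar time.

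**1. The case.** A treated patient ends participation, declines visits and accepts the call. An event starts after the patient leaves and within 16 weeks of the last dose. Section 5.2.4.2.1 makes withdrawal of participation one of its two definitions of end of study, so its second bullet applies from then on.

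**2. What each text does with the event.**

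| Event | 3.2.4.1 via 6.1.3 | 5.2.4.2.1, after end of study | Vital Status paragraph | 5.2.4.2.2, to sponsor | Counted under 7.1.1 |
|---|---|---|---|---|---|
| Cancer | eCRF, if possible | report, not in CRF | mandatory | yes | yes |
| Unrelated death | eCRF, if possible | not listed | mandatory | yes | yes |
| Drug-related SAE or AESI | eCRF, if possible | report, not in CRF | mandatory | yes | yes |
| Unrelated non-fatal SAE, not cancer | eCRF, if possible | not listed | not listed | yes | yes |
| Unrelated AESI | eCRF, if possible | not listed | not listed | yes | yes |
| Other non-serious AE | eCRF, if possible | not listed | not listed | only if relevant to a reported SAE or AESI | yes |

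Every row is counted in the analysis. The first two columns disagree on CRF entry in every row. In the last three rows the two parts of 5.2.4.2.1 require nothing at the call.

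**3. Do the cross-references settle it?** No. Sections 3.2.4.1 and 5.2.4.2.1 refer to each other, and neither says which prevails.

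**4. Patients who stop medication only.** For them the first bullet of 5.2.4.2.1 still requires all AEs and AESIs in the CRF to 16 weeks after the last dose. The Vital Status paragraph names them too but does not cancel that duty. The group is nearly empty, since treatment is one infusion and an optional second a week later (4.1.2).

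**5. How much of the window can rest on the call.** Inputs are the nominal Flow Chart days, with visit windows ignored. The TEAE window is 113 − 1 = 112 days after one dose and 120 − 1 = 119 days after two. The stretch is the final day minus the day of the last attended visit.

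| Doses | Last visit | Stretch | Share of window |
|---|---|---|---|
| One | Day 8 | 113 − 8 = 105 days | 105/112 = 94% |
| One | Day 29 | 113 − 29 = 84 days | 84/112 = 75% |
| Two | Day 15 | 120 − 15 = 105 days | 105/119 = 88% |
| Two | Day 36 | 120 − 36 = 84 days | 84/119 = 71% |

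These are calendar times, not lost events. The early end-of-study visit in footnote 2 shortens them whenever it takes place after the last scheduled visit.

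**The case against.** The strongest reply is that the texts can be read together. Section 3.2.4.1 makes a broad request covering all AEs, and the Vital Status paragraph sets a mandatory floor for the gravest. That paragraph lacks the word that closes the list in the second bullet of 5.2.4.2.1, and footnote 2 also speaks of a minimum. On this reading nothing is lost if 3.2.4.1 is followed in full. This stands as a possible reading of the list. But no text states it, and it does not remove the conflict over CRF entry after withdrawal of participation.

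The practical limits also stand. Footnote 2 asks for an early end-of-study visit, at which AEs are a scheduled item. Section 6.1.3 allows phone and video visits with full AE recording. Section 5.2.4.2.2 sends SAEs and AESIs to the sponsor whatever their cause. What is left is mainly non-serious AEs, plus CRF entry of unrelated events, in patients who leave, decline other contact and accept one call.

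A reader might infer more than the documents support:

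- **That 71% to 94% of events are lost.** Those shares are follow-up time, and they ignore the early end-of-study visit.
- **That the protocol is silent on CRF entry.** It is contradictory: 3.2.4.1 points to the eCRF through 6.1.3, while 5.2.4.2.1 bars entry.
- **That unrelated SAEs and AESIs never reach the sponsor.** Section 5.2.4.2.2 covers those known to the investigator.
- **That all early stoppers are affected.** Full collection already binds those who stop medication only.

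**Conclusion.** The conflict is real, and minor. It concerns patients who end participation, decline visits and accept the 16-week call. If a site applies 5.2.4.2.1 and its Vital Status paragraph as written, non-serious TEAEs go uncollected, and unrelated AESIs and unrelated non-fatal SAEs other than cancer do not enter the CRF, although the analysis counts all of them.

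The effect on TEAE, SAE or AESI incidence cannot be computed, because the protocol gives no early-stopping rate and no expected AE rate for this trial. It is zero where sites follow 3.2.4.1 in full. It is probably small in any case, because the subgroup should be small. The analyses are descriptive with no hypothesis test, so no inference is at risk.

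The conclusion assumes that ending participation in 3.2.4.1 is the same as withdrawal of participation in 5.2.4.2.1; the protocol does not separate the two. If a patient who accepts the call were held not to have withdrawn, the first bullet of 5.2.4.2.1 would require all AEs to 16 weeks. The shorter Vital Status list would then still need to be marked as a minimum.

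**What to change.** 1. In the Vital Status paragraph of 5.2.4.2.1, state that the listed events are a minimum. Add that, within what the patient agrees to, the call asks for all new AEs, SAEs and AESIs with onset up to 16 weeks after the last dose and for changes in ongoing AEs, and that these are entered in the eCRF regardless of relationship or seriousness.
2. In the AE Collection bullets of 5.2.4.2.1, state that for patients who agree to the call the bar on CRF entry applies only to events with onset more than 16 weeks after the last dose. If the call is not achieved, collection ends at the last contact. Tying the rule to onset date keeps it workable when the call is late.
3. Make 3.2.4.1 and Flow Chart footnote 2 refer to the sentence in item 1.

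The cost is a few sentences in an amendment and a few more minutes on a call that is already planned. The downside is longer recall of non-serious events: 84 to 105 days (84/7 = 12 to 105/7 = 15 weeks) for the last visits tabulated above, and less when an early end-of-study visit takes place. Reporting how many treated patients have complete 16-week AE follow-up would be useful, but it is optional and not part of the fix.

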##### 5.2.4.2.2 AE reporting to the sponsor and timelines

The investigator must report SAEs, AESIs, and non-serious AEs which are relevant for the reported SAE or AESI, on the BI SAE form to the sponsor's unique entry point within 24 hours of becoming aware of the event. The country-specific process will be specified in the ISF. The same timeline applies if follow-up information becomes available. In specific occasions, the investigator could inform the sponsor upfront via telephone. This does not replace the requirement to complete and send the BI SAE form.

With receipt of any further information related to these events, a follow-up SAE form must be provided. For follow-up information the same rules and timeline apply as for initial information. All (S)AEs, including those persisting after individual patient's end of trial must be followed up until they have resolved, have been assessed as "chronic" or "stable", or no further information can be obtained.

#### 5.2.4.2.3 Pregnancy

In rare cases, pregnancy might occur in a clinical trial. Once a patient has been enrolled in the clinical trial and has taken trial medication, the investigator must report any drug exposure during pregnancy in a trial participant immediately (within 24 hours) by means of Part A of the Pregnancy Monitoring Form to the sponsor's unique entry point.

The outcome of the pregnancy associated with the drug exposure during pregnancy must be followed up and reported to the sponsor's unique entry point on the Pregnancy Monitoring Form for Clinical Studies (Part B).

The ISF will contain the Pregnancy Monitoring Form for Clinical Studies (Part A and B).

As pregnancy itself is not to be reported as an AE, in the absence of an accompanying SAE and/or AESI, only the Pregnancy Monitoring Form for Clinical Studies and not the SAE form is to be completed. If there is an SAE and/or AESI associated with the pregnancy an SAE form must be completed in addition.

## 6. INVESTIGATIONAL PLAN

### 6.1 DETAILS OF TRIAL PROCEDURES AT SELECTED VISITS

#### 6.1.1 Screening period

After informed consent, patients considered for this trial will undergo an eligibility evaluation. Laboratory tests, must be conducted locally to ensure patients meet the inclusion and exclusion criteria described in sections [3.2.2](#) and [3.2.3](#), which include:

- Liver function tests (AST, ALT and alkaline phosphatase)
- Complete blood count, with differential
- Pregnancy (blood) test in women of childbearing potential
- TB test, to rule out active disease
  - In accordance with details in section [4.2.1.1](#), if TB test results are not available at the time of infusion, patients may receive treatment (provided they meet all other inclusion/exclusion criteria) as long as the investigator has ruled out active disease based on available documented history (i.e. negative for active TB) within 3 months prior to infusion.
- Possible HIV and viral hepatitis tests, to rule out active disease in presence of clinical signs or suspicion
  - If HIV and viral hepatitis test results are not available at the time of infusion, patients may receive treatment (provided they meet all other inclusion/exclusion criteria) as long as the investigator has ruled out active disease based on available documented history (i.e. negative for HIV and viral hepatitis) within 3 months prior to infusion.

Once consent is obtained, the patient is considered to have started the screening process and is assigned a unique patient number in the IRT system. The patient is to be recorded on the enrolment log and registered in the IRT system as a screened patient. All patients who are screened must be registered in the IRT system.

Demographics, baseline conditions (including any findings of the physical examination and vital signs evaluation) and concomitant therapies will be recorded in the eCRF.

If the patient meets all eligibility criteria, infusion of spesolimab may proceed immediately.

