**\*The day of first study drug administration = Day 1. All subsequent study Days are counted from this Day 1.**

- 1: Visit 1 and Visit 2 can be on the same day if required (see also footnote 7).
- 2: Should a patient prematurely discontinue from the treatment, every effort should be made to keep the patient in the trial and complete all of the remaining study visits. If a patient is not willing to follow the whole visit schedule, the EOS Visit (Visit 5) should be conducted at 16 weeks after the last spesolimab administration at a minimum. If patients refuse to return to the study site, early EoS visit should be completed at the timing of prematurely discontinuation and then at least safety information should be collected by phone at 16 weeks after the last spesolimab administration.
- 3: In case of persistent flare symptoms after a single infusion of spesolimab, a second IV dose can be administered at Visit 3 (Day 8). When a second dose is administered at investigator's discretion, IRT call is required at Visit 3 and all procedures/measurements listed for Visit 3 should be performed prior to dosing.
- 4: If patients receive a second i.v. dose of spesolimab at Visit 3 (Day 8), additional visit (Visit 3-2) is required at Day 15 and Visit 4 and Visit 5 (EoS) should be shifted by 1 week, i.e. Visit 4 at Week 5 and Visit 5 at week 17.
- 5: Physical examination, vital signs and safety laboratory test shown with parentheses "(X)" are optional and will be performed according to standard clinical practice and when deemed appropriate by the investigator.
- 6: Infection testing includes tuberculosis, hepatitis B, hepatitis C, and HIV assessments (see [Table 5.2.3:1](#)).
- 7: These procedures do not need to be repeated/performed when V1 and V2 are performed on the same day.
- 8: Only applicable for women of childbearing potential. S – serum pregnancy test.
- 9: Safety laboratory tests at screening visit (Visit 1) include liver function test, haematology test, infection screening test and if a woman of childbearing potential, pregnancy test, and will be performed locally. Please refer to Section [5.2.3](#) for further details.

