#### 5.2.3 Safety laboratory parameters

The laboratory tests listed in [Table 5.2.3:1](#) are to be collected at the trial sites and assessed by the investigators prior to study drug infusion for eligibility confirmation.

Any additional laboratory testing during the trial is optional and should be performed at the discretion of the investigator in accordance with the current standard of care, which may yield useful information for the management and safety evaluation of the patient.

Clinically relevant abnormal findings as judged by the investigator will be reported as adverse events (please refer to section [5.2.4](#)).

In case the criteria for DILI are fulfilled, a number of additional measures will be performed (please see section [5.2.4.1.4](#) and the DILI Checklist provided in the ISF).

Table 5.2.3:1 Laboratory tests to be assessed at V1 prior to i.v. administration (Local Labs)

Category	Test name
Haematology	Haematocrit Haemoglobin Red blood cell count (RBC) White blood cell count (WBC) Platelet count
WBC differential (relative and absolute)	Neutrophils, eosinophils, basophils, monocytes, lymphocytes
Enzymes	Aspartate transaminase (AST/GOT) Alanine transaminase (ALT/GPT) Alkaline phosphatase
Substrates	Total bilirubin
Infection testing	Hepatitis B Surface Antigen Hepatitis B Surface Antibody Hepatitis B core Antibody HBV-DNA (quantitative)  QuantiFERON® TB or T-Spot®  Hepatitis C Antibodies HIV-1, and HIV-2 Antibody
Serum Pregnancy test (only for female patients of childbearing potential)	Human Serum Chorionic Gonadotropin

 An HBV-DNA test should be conducted if Hepatitis B core Antibody and/or Hepatitis B Surface Antibody is positive and Hepatitis B Surface Antigen is negative. If HBV DNA level is undetectable (<2.1 log copies/mL) at screening, the patient can participate in this trial.

 If the 1st QuantiFERON® TB or T-Spot® test result is indeterminate, a retest should be performed.

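### Section 6.1.1 ties HIV and viral hepatitis tests to clinical signs, while the Flow Chart and Section 5.2.3 require them in every patient before infusion

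*Combined protocol and SAP*

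**What the plan says.** Three places in the protocol govern HIV and viral hepatitis testing at screening.

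- **Flow Chart.** Infection testing has a plain X at Visit 1. Footnote 6 defines it: "Infection testing includes tuberculosis, hepatitis B, hepatitis C, and HIV assessments", with a pointer to Table 5.2.3:1. Footnote 9 adds: "Safety laboratory tests at screening visit (Visit 1) include liver function test, haematology test, infection screening test", with a pointer to Section 5.2.3. Optional items are marked differently. Footnote 5 applies to "Physical examination, vital signs and safety laboratory test shown with parentheses", and infection testing carries none.
- **Section 5.2.3.** The tests in Table 5.2.3:1 include hepatitis B surface antigen, surface antibody and core antibody, hepatitis C antibodies and HIV-1/2 antibody. They "are to be collected at the trial sites and assessed by the investigators prior to study drug infusion for eligibility confirmation". What is left to discretion is testing beyond that list: "Any additional laboratory testing during the trial is optional and should be performed at the discretion of the investigator". Footnote 1 of the table sets the hepatitis B rule: "An HBV-DNA test should be conducted if Hepatitis B core Antibody and/or Hepatitis B Surface Antibody is positive" and surface antigen is negative. If HBV-DNA is then undetectable (<2.1 log copies/mL) "at screening, the patient can participate in this trial".
- **Section 6.1.1.** The lead-in makes local laboratory tests obligatory for checking eligibility, but one bullet reads "Possible HIV and viral hepatitis tests, to rule out active disease in presence of clinical signs or suspicion". A sub-bullet lets a patient be treated when these results are not available at infusion, provided active disease has been ruled out from a documented history, negative for HIV and viral hepatitis, within the previous 3 months.

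**The concern.** A site cannot tell from the text whether a patient with no signs of HIV or hepatitis must be tested. Two places say yes for everyone. Section 6.1.1, which describes the screening procedure step by step, says only when there are signs or suspicion. No statement says which text prevails.

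An eligibility safeguard is at stake. Viral hepatitis and HIV infection are exclusion criterion 5 in Section 3.2.3. Excluding such patients is part of the infection-risk mitigation in Table 1.4:1, and HBV reactivation is among the adverse events of special interest in Section 5.2.4.1.4. The HBV-DNA rule is stated only in footnote 1 of Table 5.2.3:1, and it starts from serology. A trigger based on clinical signs does not lead to it in a patient without symptoms.

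Time pressure adds to this. Visits 1 and 2 may fall on the same day, and 6.1.1 lets infusion proceed as soon as eligibility is met. Laboratory tests after screening are optional, so Visit 1 is the only visit at which the protocol requires this check.

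**Working it through.** No arithmetic applies: the trial is descriptive, has no recruitment goal, and attaches no figure to this point. The check is a comparison of texts, followed by a walk through the possible cases.

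**Step 1: the instructions side by side**

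| Place | Who is tested for HBV, HCV and HIV | Timing |
|---|---|---|
| Flow Chart, footnotes 6 and 9 | Every patient | Visit 1 |
| Section 5.2.3, Table 5.2.3:1 | Every patient | Collected and assessed before infusion |
| Section 6.1.1 bullet | Patients with signs or suspicion | Screening |

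The first two rows are not independent, because the Flow Chart footnotes point to Section 5.2.3 and its table. They agree with each other and disagree with the third.

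**Step 2: can the bullet be read in harmony with the rest?** It could be meant as extra, sign-driven testing on top of a universal screen. But 6.1.1 lists no other HIV or hepatitis test that it could add to. In the same list, liver tests, blood count and TB test carry no such condition, and the pregnancy test is limited only to women of childbearing potential. The harmonising reading is weak.

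**Step 3: a patient without signs, case by case**

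1. *The site follows the Flow Chart and 5.2.3.* Serology is drawn and footnote 1 can be applied. No gap, apart from results not back by infusion.
2. *The site follows the 6.1.1 bullet, and the history shows surface antigen, core antibody and surface antibody all negative within 3 months.* Footnote 1 would not call for HBV-DNA. No gap for hepatitis B.
3. *The site follows the bullet, and the recent negative history lacks core or surface antibody.* The fallback can be met as worded, because it names no markers. Footnote 1 cannot be fully evaluated. This is a gap.
4. *The site follows the bullet, and there is no recent negative record.* The fallback speaks of results not being available, which also describes a test never drawn. On that reading the patient may not be dosed. A gap arises only if the site takes the bullet as waiving the test altogether.

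**Step 4: the backstops.** Section 4.1.2 assigns kits only after all criteria are verified. Section 8.3.1 requires source evidence for each criterion and says that missing records do not make a patient eligible. It does, however, count documented verbal feedback from the patient as a record. These provisions narrow cases 3 and 4 but do not close them.

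**The case against.** The strongest reply is that omission is unlikely. A site would have to overlook the Flow Chart, two of its footnotes and Section 5.2.3, and follow one bullet whose own lead-in makes testing obligatory. The footnotes name Section 5.2.3 as the place for laboratory detail, which works as a pointer even though no precedence is stated. The 3-month condition means that 6.1.1 gives no clear licence to dose an untested patient with no recent negative record. Monitoring against source data (Section 8.3.2) is a further check. All of this stands, and it limits the exposure to cases 3 and 4 above. It does not remove the contradiction: one of the texts must change whichever policy the sponsor intends.

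A second reply is that rewording the bullet does not guarantee that HBV-DNA is known before dosing. That is correct. While the fallback remains, a patient can be treated before results return. The rewording ensures that the tests are drawn.

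A reader might infer that the protocol has dropped HIV and hepatitis screening, or that every patient without symptoms may be dosed untested. The documents do not support either. The tests remain scheduled for all patients, exclusion criterion 5 must still be evidenced, and the fallback requires a recent documented negative history.

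**Conclusion.** The point holds as an internal inconsistency in current text on an eligibility safeguard, with limited exposure. The wording conflict itself is certain. The consequence is conditional: it needs a site that works from the 6.1.1 bullet and a patient without signs. It then needs either a recent negative history without core or surface antibody, or a reading of the bullet as a waiver.

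No size can be given. The documents state neither a target number of patients nor how often patients are surface-antigen negative and antibody positive, and the number affected could be zero. The primary and secondary endpoints and the descriptive analyses are unaffected.

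The conclusion assumes that universal testing is the intended policy, as the Flow Chart and Section 5.2.3 indicate. If sign-driven testing was intended, those two places need correcting instead.

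**What to change.** - **Section 6.1.1, HIV and hepatitis bullet.** Delete *Possible* and the clause tying the tests to clinical signs or suspicion. State that the HBV, HCV and HIV tests of Table 5.2.3:1, with HBV-DNA per footnote 1, are drawn in all patients at Visit 1.
- **Section 6.1.1, sub-bullet.** Keep the 3-month fallback, stating that it applies when the tests have been drawn but results are not yet available at infusion.
- **Section 5.2.3 and Flow Chart footnote 6.** Add a cross-reference to that fallback, which neither mentions now.

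The sponsor may also wish to name the hepatitis B markers that a qualifying history must contain. This would address case 3 directly, but could delay dosing in an urgent flare, so it is left as an option.

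The cost is a small amendment needing IRB and competent authority approval under Section 8.1. No test is added, since all are already scheduled at Visit 1. The change slightly narrows the fallback, which at present does not separate tests not drawn from results not back. HBV-DNA may still be unknown at dosing for patients treated under the fallback.
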